6.4 SAFETY ANALYSIS SET

The Safety Analysis Set (SAS) will consist of all patients who receive at least one dose of tofacitinib. All reporting of safety data will utilize the SAS.

6.5 PER PROTOCOL ANALYSIS SET

Patients with data collected at scheduled visits, which fall within the defined visit windows (see section 12.1.1) will be assigned to the Per-Protocol Analysis Set (PPAS).

6.6 SUBGROUPS

The following subgroups will be considered for the analysis of the secondary endpoints if sufficient numbers of patients are available.

:

- 1) Sequence of therapy, where subgroups (with treatment labels as defined in 2.2.1.2) are:
 - a) Patients who were on tofacitinib as a Monotherapy throughout the study.
 - b) Patients who were on tofacitinib as a Monotherapy and switched to tofacitinib in combination with MTX.
 - c) Patients who were on tofacitinib in Combination with MTX throughout the study.
 - d) Patients who started on tofacitinib in Combination with MTX and switched to tofacitinib as a Monotherapy.

Note: Only a patient's first switch will be used to classify them into a subgroup.

If above classification is too granular, the following subgroups will be used for sequence of therapy:

- a) Patients who were on tofacitinib as a Monotherapy throughout at least 60% of their observational time
 - b) Patients who were on tofacitinib as a Combination with MTX throughout at least 60% of their observational time
-
- 2) Medication history of RA treatment where the subgroups are:
 - a) Those on 2nd line treatments prior to starting study.
 - b) Those on 3rd line treatments prior to starting study.
- The eCRF will be referred to for a list of drug names for each category.
- 3) Patient's Switch Status, where the subgroups are:
 - a. Patients with a treatment step- up as defined in section 7.1.1: switch up
 - b. Patients that remain on tofacitinib treatment or patients with a treatment step-down: no switch up
 - 4) Number of Treatment Escalations (as defined in section 7.1.1):
 - a) Patients with no treatment escalations.

- b) Patients with 1 treatment escalation.
- c) Patients with 2 treatment escalations.
- d) Patients with 3 or more treatment escalations.

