7.9.2.2. Secondary Analysis

7.9.2.2.1. Time to Event Analysis

Time to event endpoints will be investigated using Kaplan-Meier methodology and, where appropriate, Cox-Proportional Hazards modelling will be used to look at differences in event rate between sub-groups. The time to event will be summarised in terms of medians and confidence intervals. Kaplan-Meier plots of the time to event over the study duration will be presented.

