9.2.5 SUBGROUP ANALYSIS

In addition to the analyses described above secondary endpoints will be analysed split by the subgroups described in section 6.6, as appropriate.

If additional subgroup analyses are needed, the details will be included as an amendment to this SAP prior to database release.

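### Three of the four SAP subgroup families are defined by events after baseline and none by starting regimen, so the secondary-endpoint tables describe patients selected on their later course

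*SAP*

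**What the plan says.** SAP 6.6 names four subgroup families for the secondary endpoints, subject to sufficient patient numbers.

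- **Therapy sequence.** Group (a) is "Patients who were on tofacitinib as a Monotherapy throughout the study" and group (c) is "Patients who were on tofacitinib in Combination with MTX throughout the study". Groups (b) and (d) are patients who changed from one of these regimens to the other, with the rule that "Only a patient's first switch will be used to classify them into a subgroup". If this proves too granular, two fallback groups replace it, the first being "Patients who were on tofacitinib as a Monotherapy throughout at least 60% of their observational time"; the second is the same rule for combination with MTX.
- **Medication history.** 2nd-line or 3rd-line treatment before the study.
- **Switch status.** Patients with a step-up, against "Patients that remain on tofacitinib treatment or patients with a treatment step-down: no switch up".
- **Number of escalations.** "Patients with no treatment escalations", then one, two, and three or more. SAP 7.1.1 counts terminations, step-ups and step-downs all as escalations.

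SAP 9.2.5 states that "secondary endpoints will be analysed split by the subgroups described in section 6.6, as appropriate". The summary table in SAP 9.2.6 enters all four families against LDA, remission, DAS28, morning stiffness, FFbH, functional remission, EQ-5D, FACIT-Fatigue and satisfaction. It leaves the subgroup cell blank for time to first escalation and for drug survival.

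SAP 7.1.1 says that every patient begins on tofacitinib either alone or with MTX, and Protocol 7.6.5 has the regimen documented from Visit 1. No subgroup in 6.6 uses that starting regimen.

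**The concern.** A subgroup is easiest to read when membership is settled before the outcome is measured. Here a Month 3 LDA rate would be tabulated by events that may happen at Month 18. If poor response leads to escalation or stopping, patients who stay on one regimen or never escalate are a favourably selected set, and their early results look better partly because of how the group was formed. The sponsor expects such a link: Protocol 7.7 assumes a coefficient of −2.303 for the effect of a DAS28 change above 1.8 on the escalation rate, a hazard ratio (HR) of exp(−2.303) = 0.10.

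Readers of side-by-side columns for monotherapy and combination with MTX will tend to take a difference as a regimen effect. Final results are intended for journal publication (Protocol 10.1). Neither document warns about grouping on later events. Protocol 7.12 discusses selection into treatment and into the study, which is a different matter.

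**Working it through.** The plan gives no figure for these tables, so there is none to reproduce. The check has two parts.

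**1. Who fits which group, on the literal wording**

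Follow-up runs to 24 months even after tofacitinib is left (SAP 3.1).

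- *Sequence (a) to (d):* a patient who stops tofacitinib before any regimen switch was not on either regimen throughout the study and did not change between them, so fits none of the four.
- *60% fallback:* 0.6 × 24 = 14.4 months. A patient followed for 24 months who leaves tofacitinib before month 14.4 cannot reach 60% on either regimen.
- *Switch status:* a patient who terminates tofacitinib with no step-up or step-down neither remains on it nor steps up or down, so fits neither group.
- *Medication history:* settled before baseline and not affected.

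**2. Size of the selection, under stated assumptions**

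From the documents: 60% of patients reach a DAS28 change above 1.8 (Protocol 7.7), here called responders.

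Assumed: the same 60% in both starting regimens; HR of stopping tofacitinib 0.5 for responders; 24-month persistence P of 70% or 50%; probability s of switching between monotherapy and combination of 10% or 30% over 24 months, before allowing for stops; constant hazards. There is no true difference between regimens.

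*Persistence alone.* Let x be the 24-month persistence of responders; that of non-responders is then x². So P = 0.6x + 0.4x², and the responder share among persisters is 0.6x / P.

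- P = 0.70: x = [−0.6 + √(0.36 + 1.6 × 0.70)] / 0.8 = 0.771; share = 0.6 × 0.771 / 0.70 = 66%.
- P = 0.50: x = [−0.6 + √(0.36 + 1.6 × 0.50)] / 0.8 = 0.596; share = 0.6 × 0.596 / 0.50 = 72%.

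If switching is unrelated to response, its factor cancels. Both 'throughout' groups then show the same inflated share, 66% v 66% or 72% v 72%, and no false contrast appears.

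*Switching that depends on response.* Suppose non-responders add MTX three times as often as responders, and responders drop MTX three times as often as non-responders. Let c = −ln(1 − s). The cumulative switching hazards for responders (aR) and non-responders (aN) are:

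- starting on monotherapy: aR = c/1.8, aN = 3c/1.8 (1.8 = 0.6 × 1 + 0.4 × 3);
- starting on combination: aR = 3c/2.2, aN = c/2.2 (2.2 = 0.6 × 3 + 0.4 × 1).

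Responder share in the 'throughout' group = 0.6x·exp(−aR) / [0.6x·exp(−aR) + 0.4x²·exp(−aN)].

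For P = 0.70 and s = 0.10, c = 0.1054:

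- monotherapy: 0.4361 / (0.4361 + 0.1993) = 68.6%;
- combination: 0.4005 / (0.4005 + 0.2265) = 63.9%.

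| Persistence | Switching | Monotherapy throughout | Combination throughout | False gap (points) |
|---|---|---|---|---|
| 70% | 10% | 68.6% | 63.9% | 5 |
| 70% | 30% | 74.3% | 58.5% | 16 |
| 50% | 10% | 73.9% | 69.6% | 4 |
| 50% | 30% | 78.9% | 64.5% | 14 |

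A simulation of 400,000 patients per regimen agrees with these to within 0.1 point. In it, 25% to 48% of starters stop before any switch and so fit none of groups (a) to (d).

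*Looser reading.* If 'throughout' means throughout the patient's own time on tofacitinib, the simulated gap under response-dependent switching runs from 62% v 58% to 66% v 53%.

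*Sensitivity to the HR.* At HR 0.75 the share among persisters is 63% (P = 0.70) to 65% (P = 0.50). At HR 1.0 it stays at 60%. If the planning value of 0.10 for escalation is borrowed for stopping, with the planned LDA factor also included, it is 78% to 93%.

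*Grouped by starting regimen.* All starters: 60% v 60%, with nobody outside the groups.

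**The case against.** The strongest reply is that these tables carry little inferential weight. SAP 5 says data are summarised descriptively, SAP 9.1.6 rules out formal comparison between treatment groups, the subgroups are conditional on numbers, and the primary model does not use them. That stands, and it limits the harm to interpretation.

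The aim is also to learn what drives treatment decisions. Describing disease activity or satisfaction in patients who did and did not later escalate serves that aim. This stands too, and is a reason to keep the tables with a label.

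'Throughout the study' may mean throughout tofacitinib exposure: the secondary analyses use only on-tofacitinib data (SAP 9.2.3), and the treatment labels in SAP 3.2.1.2 omit the word. So the exclusion of stoppers is an ambiguity to settle and not an established fact. The looser reading reduces the false gap without removing it.

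Three stronger readings are tempting, and the documents do not support them.

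- *That drug survival will be split by these groups, making survival 100% by construction in the 'throughout' groups.* SAP 9.2.5, taken alone, could cover it, but it says as appropriate, and the cells for drug survival and time to first escalation in 9.2.6 are blank.
- *That these groups will be formally compared.* Protocol 7.9.2.2.1 says "Cox-Proportional Hazards modelling will be used to look at differences in event rate between sub-groups", but only where appropriate and without naming any subgroup. SAP 9.1.2 plans descriptive and Kaplan-Meier output only.
- *That a monotherapy-versus-combination difference arises automatically.* Persister selection raises both groups. A gap also needs switching or stopping to depend on response or to differ by regimen.

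**Conclusion.** The point holds as a problem of interpretation in descriptive secondary tables. Three of the four subgroup families are selected on later course, the starting regimen is not used, and the literal definitions leave some tofacitinib stoppers unclassified. No test, error rate or primary result is affected.

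The size rests on assumptions about persistence, switching and the link between response and stopping, none of which the documents give. Under those used here, the false monotherapy-versus-combination gap runs from zero, when switching is unrelated to response, to 16 percentage points, when it is strongly related. Dependence on response is plausible, because SAP 7.1.1 treats dropping from combination to monotherapy as a step-down and Table 12.2 treats adding a csDMARD to tofacitinib as a step-up, but it is not shown.

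**What to change.** - Make the regimen at tofacitinib start (monotherapy, or combination with MTX) the main therapy subgroup for the secondary endpoints in SAP 6.6 and 9.2.6.
- Keep the sequence, switch-status and escalation-count tables. Label them as describing patients selected on later course, or use a landmark: status at a fixed visit such as Month 3 or Month 6, with outcomes measured afterwards.
- Define 'throughout' and 'observational time' for patients who stop tofacitinib, and show how many patients fall outside every group.
- State in 9.2.5 that drug survival and time to first escalation are not split by the post-baseline groups, in line with the blank cells in 9.2.6.
- Show numbers at risk at each visit. Starting regimen does not cure the separate selection from using on-tofacitinib data only: with equal stopping in both regimens, the Month 24 shares in the example would be 66% v 66% or 72% v 72%, equal but not 60%.

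The cost is SAP wording and a few extra tables on data already collected. SAP 9.2.5 already provides for added subgroup analyses by amendment before database release.

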7 ENDPOINTS AND COVARIATES

7.1 EFFICACY/ EFFECTIVENESS ENDPOINT(S)

7.1.1 PRIMARY ENDPOINTS

Number and timing of treatment escalations of tofacitinib patients in 24 months, where Treatment Escalation in this study is defined as a switch to another DMARD or combination of DMARDs when compared to the last visit.

The following types of escalations will be distinguished:

1. Treatment **Termination**, which is the termination of a DMARD (or multiple when on combination therapy) without starting a new DMARD therapy. Premature study terminations (without documented treatment termination) will not be considered treatment terminations.
2. Treatment **Step-up** which is an increase from the current treatment regime towards e.g. a combination of DMARDs
3. Treatment **Step-down**, which is a de-escalation from the current treatment regime, e.g. from combination therapy to monotherapy

Patients start their therapy at baseline with tofacitinib either in Monotherapy or in Combination therapy with MTX. Subsequent therapy changes are documented on eCRF instrument “Rheumatologische Medikation“ by:

- adding additional DMARDs on top of the current therapy
- stopping the current DMARD in monotherapy and adding a new DMARD
- stopping one of multiple DMARDs when on combination therapy
- stopping one of multiple DMARDs when on combination therapy and adding a new DMARD
- stopping all DMARDs and not starting a new therapy. The escalation types depend on the combination of DMARD classes (tsDMARD vs bDMARD vs TNFi vs csDMARD). The eCRF does not explicitly distinguish between tsDMARD vs bDMARD vs TNFi, but combines all rheumatic medications belonging to the above classes under

tsDMARD/bDMARD. For the definition of treatment escalations, the following assignment of rheumatic medication to DMARD classes will be done:

tsDMARDs:

- baricitinib
- upadacitinib
- filgotinib

TNFi:

- etanercept
- adalimumab
- certolizumab
- golimumab
- infliximab

bDMARDs (excluding TNFi):

- abatacept
- rituximab
- anakinra
- tocilizumab
- sarilumab

For details of treatment escalations, e.g., which DMARD class addition or reduction leads to a particular escalation type, see table 12.2 in section 12.1.2.

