12.1.2 DEFINITION OF TREATMENT ESCALATIONS

Table 11.2 provides an overview of all possible treatment switch combinations relevant for the analysis of the primary endpoint and defines the type of escalations, e.g., whether the treatment switch relates to a step-up, step-down or termination.

Table 12.2: Definition of treatment escalations

Therapy*	Mono Tofa	Mono tsDMARD	Mono csDMARD	MonoTNFi	Mono bDMARD	Combo+ csDMARD	Combo tsDMARD +csDMARD	ComboTNFi +csDMARD	Combo bDMARD+ csDMARD	Therapy Stop
MonoTofa	-	Step-up		Step-down	Step-up	Step-up	Step-up	Step-up	Step-up	Treatment termination
Mono tsDMARD	Step-up	Step-up if different tsDMARD		Step-down	Step-up	Step-up	Step-up	Step-up	Step-up	Treatment termination
Mono csDMARD	Step-up	Step-up	Step-up if different csDMARD		Step-up	Step-up	Step-up	Step-up	Step-up	Treatment termination
MonoTNFi	Step-up	Step-up		Step-down	Step-up if different TNFi	Step-up	Step-up	Step-up	Step-up	Treatment termination
Mono bDMARD	Step-up	Step-up		Step-down	Step-up	Step-up if different bDMARD	Step-up	Step-up	Step-up	Treatment termination
Combo+ csDMARD	Step- down	Step-up		Step-down	Step-up	Step-up	Step-up if different csDMARD	Step-up	Step-up	Treatment termination
Combo tsDMARD +csDMARD	Step-up	Step-up if different tsDMARD; Step-down otherwise		Step-down	Step-up	Step-up	Step-up if different tsDMARD or csDMARD	Step-up	Step-up	Treatment termination
Combo TNFi + csDMARD	Step-up	Step-up		Step-down	Step-down, if same TNFi, Step-up if different TNFi	Step-up	Step-up	Step-up if different csDMARD/TN Fi	Step-up if different bDMARD or csDMARD	Treatment termination
Combo bDMARD+ csDMARD	Step up	Step up		Step down	Step up	Step down if same bDMARD; Step-up otherwise	Step up	Step up	Step up	Step up if different bDMARD or csDMARD
*) Definitions:			Mono tsDMARD= Monotherapy any tsDMARD other than Tofa Mono csDMARD= Monotherapy any csDMARD Mono TNFi= Monotherapy any TNFi Mono bDMARD= Monotherapy any bDMARD other than TNFi Combo Tofa= Combination therapy tofacitinib with any csDMARD Combo csDMARD= Combination therapy tofacitinib + any csDMARD				Combo tsDMARD + csDMARD= Combination therapy tsDMARD other than tofacitinib + any csDMARD Combo TNFi + csDMARD= Combination therapy any TNFi+ any csDMARD Combo bDMARD + csDMARD= Combination therapy bDMARD other than TNFi+ anycsDMARD			

PPD

PPD

PPD

LEGAL DISCLOSURE

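### Table 12.2 does not separate one csDMARD from two, so withdrawing one of two csDMARDs is uncoded or a step-up, but never a step-down

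*SAP*

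**What the plan says.** SAP 7.1.1 gives the starting point: "Patients start their therapy at baseline with tofacitinib either in Monotherapy or in Combination therapy with MTX". It then lists how later changes are documented in the eCRF. The first is "adding additional DMARDs on top of the current therapy" and the third is "stopping one of multiple DMARDs when on combination therapy".

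The same section defines three escalation types in prose. Step-up is an increase in the regimen. Step-down is a change "which is a de-escalation from the current treatment regime, e.g. from combination therapy to monotherapy". Termination is a change "which is the termination of a DMARD (or multiple when on combination therapy) without starting a new DMARD therapy". For the detail of "which DMARD class addition or reduction leads to a particular escalation type, see table 12.2 in section 12.1.2", the reader is sent to the appendix.

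SAP 12.1.2 says that the table "provides an overview of all possible treatment switch combinations relevant for the analysis of the primary endpoint". Its states are five monotherapies (tofacitinib, other tsDMARD, csDMARD, TNFi, other bDMARD), the four targeted classes each combined with a csDMARD, and therapy stop. The combination states are defined with any csDMARD; the number of csDMARDs is not part of the definition. When a patient stays in the tofacitinib combination state, or in csDMARD monotherapy, the only code is "Step-up if different csDMARD". The other targeted combinations have matching cells that also allow only step-up.

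**The concern.** The event type is decided by the table, and the table cannot see a change in the number of csDMARDs. A reduction from two csDMARDs to one, with the targeted drug kept, is a de-escalation in ordinary terms and by the prose of 7.1.1, yet the table offers no route to step-down for it.

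The type matters because SAP 9.1.1 fits the recurrent-event model for each type as well as overall. SAP 7.1.2.1 uses step-up as the event for time to first escalation, and SAP 6.6 forms subgroups by switch-up status and by number of escalations. Two programmers working from the same SAP could code the same record differently, and the choice would be made after the data are in.

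**Working it through.** No sample size or power figure bears on this point, so the check is a trace through the table.

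**Inputs.** The starting regimens and listed changes come from SAP 7.1.1. The states, their definitions and the conditional cells come from SAP 12.1.2. The columns of the table are partly displaced in the text I worked from, so I rely only on the list of states, the definitions below the table and the conditional cells, which are legible.

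**Step 1: can the regimen arise?** A patient starts on tofacitinib plus MTX. An add-on to the current therapy may be a second csDMARD. Stopping one of several DMARDs may later remove it.

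**Step 2: trace tofacitinib + MTX + second csDMARD to tofacitinib + MTX.**

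| Reading of the table | Adding the second csDMARD | Withdrawing it |
|---|---|---|
| (a) Any csDMARD means exactly one | no destination column: uncoded | no starting row: uncoded |
| (b) One or more; any changed csDMARD set is different | step-up | step-up |
| (c) One or more; only a newly introduced csDMARD is different | step-up | uncoded |

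The right-hand column never contains step-down. The trace is the same with another tsDMARD, a TNFi or a bDMARD in place of tofacitinib. For two csDMARDs without a targeted drug, the only candidate state is Mono csDMARD, whose same-state cell is again step-up if different.

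**Step 3: compare with the table's own treatment of a lost csDMARD.** Tofacitinib combination to tofacitinib alone is step-down. So are the moves from the other targeted combinations to monotherapy with the same targeted drug. In legible cells, step-down appears only for moves into a monotherapy state.

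**Step 4: compare with the prose.** De-escalation points to step-down. The Termination wording, read literally, covers stopping one DMARD of a combination with nothing new started, so it fits too. It also fits the move from tofacitinib plus MTX to tofacitinib alone, which the table codes as step-down. Table and prose therefore conflict even where the table has a state.

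**Step 5: which outputs change?**
- Uncoded, readings (a) and (c): the withdrawal is missing from the overall model, the step-down model and the escalation count in 6.6. Under (a) the add-on is missing as well, which removes a step-up from the step-up model and possibly from the time-to-first-step-up curve and the switch-up group.
- Coded as step-up, reading (b): the step-up model gains a de-escalation and the step-down model loses one. The overall model counts one event either way.
- Under (b), a patient who followed the path in step 1 already has a step-up from the add-on, so the withdrawal is not the first one. It could be the first by a narrower route: tofacitinib is stopped and a csDMARD added, leaving two csDMARDs (a step-down if treated as Mono csDMARD), and one of them is then withdrawn.

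**The case against.** The strongest reply is that classification by DMARD class is a stated choice in 7.1.1, and that not counting csDMARDs follows from it. The listed changes are generic. The table meets them with tofacitinib alone to tofacitinib plus csDMARD and back, and neither the treatment labels in 3.2.1 nor the sequence subgroups in 6.6 mention two csDMARDs. This stands in part: the regimen is inferred from the starting therapies and the generic list, and the SAP never names it. It does not close the gap, because 12.1.2 claims full coverage and nothing in 7.1.1 rules the regimen out.

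A second reply is that, elsewhere in the table, different is contrasted with same and refers to the drug moved to. A patient who keeps MTX has not moved to a different csDMARD, so the withdrawal is uncoded and not a step-up. I accept that this is at least as natural a reading. A reader might infer that such withdrawals are plainly coded as step-ups; the documents do not settle that.

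A reader might also infer that step-up hazard ratios are pulled toward 1 by a calculable amount. The documents do not support this:
- They give no frequency of double csDMARD use and no hazard ratio for withdrawals.
- The coefficient of -0.288 for low disease activity in protocol 7.7 is assumed for any escalation, not for step-ups alone.
- Protocol 7.6.5 records lack of efficacy or intolerance as reasons for a switch, so withdrawals need not follow low disease activity.
- Under the uncoded readings, no withdrawal enters the step-up model at all.

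**Conclusion.** The point holds as a defect in the coding rule. Under every reading of Table 12.2, withdrawal of one of two csDMARDs with the targeted drug unchanged is either uncoded or a step-up. That disagrees with the step-down prose in 7.1.1 and with the table's own handling of a lost csDMARD, while the literal Termination definition gives a further answer.

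The size is unknown, and no attenuated hazard ratio should be quoted. The consequence is bounded: if the change is coded as step-up, only the type-specific results move and the overall model does not; if it is uncoded, the event is lost from both. The conclusion rests on two assumptions: that some patients receive two csDMARDs together during follow-up, and that Table 12.2 prevails over the prose, as 7.1.1 indicates.

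**What to change.** In SAP 12.1.2, add a rule that compares the drugs before and after a change. With the targeted drug unchanged or absent:
- a csDMARD gained with none lost is step-up;
- a csDMARD lost with none gained, while at least one DMARD continues, is step-down;
- an exchange of csDMARDs stays as now.

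Add a row and column for two or more csDMARDs without a targeted drug. Code it against Mono csDMARD by the same rule, and treat it like Mono csDMARD against the targeted regimens.

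In SAP 7.1.1, reword Termination so that it applies only when all DMARDs are stopped, which matches the table's Therapy Stop column.

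The rule concerns event coding only. The cost is one paragraph, one row and column and one reworded definition, settled before database lock. The drugs and their dates are already documented (protocol 7.6.5; SAP 7.1.1), so no new data are needed.
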